1.2. Methadone providers

Methadone providers will conduct the study interventions under the clinical supervision of the study master counselors. All methadone providers have been trained on basic addiction medicine and will receive further training to deliver the study interventions. We will conduct in-depth interviews with them before and after the intervention phase.

Randomization and Interventions

An investigator will stratify participants by HIV status and randomize them into two frontline interventions using REDCap, as shown in Figure 1. She will send the allocation results to the site research assistants who will then inform providers at the study clinics. This is an open label study so unblinding does not occur. Participants and their counselors, research assistants and data managers are aware of participants' assignment of intervention. Participants will receive two individual sessions of motivational interviewing with their counselors before they get into the frontline interventions and, in Week 13, before the adaptive strategies start. These sessions would boost participants' motivation for intervention and provide them with greater details of the upcoming intervention activities.

Two frontline interventions (Weeks 1-12)

- High intensity: Participants in this arm receive contingency management with the escalating-and-reset schedule throughout 12 weeks. This schedule means participants receive increasing rewards for consecutive negative UDS but if the streak of negative UDS is broken,

their rewards return to the starting level. The maximal reward value over 12 weeks is \$150 USD, equivalent to the average monthly income of our participants.

- Low intensity: Participants in this arm receive contingency management for the first six weeks with the maximal reward value of \$40 USD. For the last six weeks, they attend weekly group education sessions. The topics of group education include 1) Addiction mechanism, 2) Road to recovery, 3) Coping with triggers, 4) Boredom, 5) Building trust and 6) Relapse prevention.

Participants with four consecutive UDS negative with methamphetamine in weeks 11 and 12 are considered to be responsive to frontline interventions. Others are considered non-responsive. Responders to frontline interventions are placed in the maintenance treatment arm. Non-responders are randomized to either enhanced treatment 1 or 2.

Three adaptive strategies (Weeks 14-25)

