- Maintenance treatment: Participants receive two daily automatic unidirectional scripted SMS reminders plus one weekly self-monitoring assessment message over 12 weeks.
- Enhanced treatment 1: Participants attend 12 weekly Matrix group counseling sessions facilitated by the clinic counselors. Our Matrix intervention has the same structure, albeit it is shorter than the original 24-sessions model.
- Enhanced treatment 2: Participants receive the same Matrix intervention plus contingency management over 12 weeks.

Definition of effectiveness measures

Effectiveness measures will be assessed at 13-, 26- and 49 weeks after the first week of frontline interventions and throughout the interventions. Primary outcomes include: (1) increase in HIV viral suppression for HIV-positive participants at 26- and 49-weeks; (2) reduction in HIV risk behaviors for both HIV-positive and HIV-negative participants at 26- and 49-weeks; and (3) reduction in methamphetamine use at 13-, 26- and 49-weeks measured by UDS (point abstinence) and self-report (continuous abstinence and longest period). Secondary outcomes include: (1) adherence to antiretroviral treatment for HIV-positive participants; 2) frequency of HIV testing for HIV-negative participants; 3) heroin use with UDS; 4) opioid overdose; and, 5) quality of life.

To acquire the primary and secondary outcomes, we will assess for the following:

- HIV viral load test. At baseline, Week 13, Week 26 and Week 49, we send blood samples of HIV-positive participants to laboratories at Bach Mai Hospital in Hanoi and HCMC University of Medicine and Pharmacy Hospital in HCMC for viral load quantification.

- Drug screening. We use an FDA-approved Multi-Drug Rapid Test Panel to detect methamphetamine, opioid, and cannabis in urine twice a week throughout the intervention period and at Week 49.
- Methadone and HIV treatment. We extract methadone and HIV treatment data from participants' medical charts. Variables of interest include length of treatment, treatment regimen, medication dose and treatment adherence.

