We will use a time-varying mixed-effects model that will be fitted to the participants' common outcome measures over time. The unadjusted model will include indicators of first-stage and second-stage intervention conditions, time of the assessment (baseline, 13-, 26-, and 49-weeks), and intervention indicators-by-time interaction terms. An additional interaction term of the two intervention indicators will be included to account for any interaction effect between the first and the second stage interventions. The adjusted model will include patients' socio-demographic characteristics, drug use history, HIV-serostatus, and location as fixed effects. The mixed-effects models will include a participant-level random effect to account for repeated observations of each participant, as well as a clinic-level random effect to account for the nested nature within the clinics. We will conduct subgroup analyses among HIV-positive and HIV-negative participants. For the HIV-positive subgroup, the specific outcomes of interest include 1) HIV viral load suppression, and 2) adherence to antiretroviral treatment; and specific outcomes for HIV-negative subgroup include 1) frequency of HIV testing and 2) HIV seroconversion. Substance use will be the common outcomes in models including participants of both HIV statuses.

To assess cost-effectiveness

We will calculate Cost Effectiveness Ratios (CER) for each of the intermediate and final outcomes. The CER is in the broadest terms the difference in per capita costs of administering one intervention (C1-C2) relative to a second, divided by the difference in outcomes between the two interventions (O1-O2):

$$CER = \frac{C1 - C2}{O1 - O2}$$

For example, calculating the CER for adding contingency management to Matrix for non-responders would yield a CER equation. In calculating the CER of high vs. low intensity contingency management at the first randomization stage, the entire range of subsequent costs will be included. Costs of delivering the interventions will be derived from clinic records of time and other inputs, as well as incentive payments, thus providing an estimate of CER from the medical system perspective. We will also evaluate CERs from a societal perspective, using a broad definition of costs, including the social costs of incarceration.

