We will conduct sensitivity analyses to estimate the extent to which the CER calculation is affected by differences in assumptions about the size of the differences in intervention effect. In particular, we will determine how sensitive the CER is to assumptions that the difference in treatment effect is one standard deviation below or above the mean estimated effect size. Similarly, we will estimate the sensitivity of conclusions to costs that are one standard deviation below or above the estimated mean.

To identify the factors influencing the adoption and scale up of the model

The qualitative analysis team will read and provide a narrative summary for each transcript. A codebook will be developed based on these summaries. Memo-writing and code-refining will be conducted throughout the analysis. Iterative analyses assess convergence of patient, provider and organizational dimensions on study measures as well as the context of the policy subsystems, cross system interactions, and resource allocation.

Analysis of non-adherence and missing data

We will first describe the extent and patterns of missingness within each variable, check for associations between missing and observed data to determine the mechanism of missingness, which could be missing completely at random, missing at random, or missing not at random. Missing data will then be handled using multiple imputation (68). Appropriate imputation techniques will be chosen for the type of missing data and the statistical tools employed (69). For sensitivity analysis, we will conduct analyses with and without multiple imputations. All participants will be analyzed on an intent-to-treat basis where the study outcomes are examined based on the random intervention assignment and not on the actual intervention received or adherence to the intervention.

Interim analyses

There is no planned interim analysis as the behavioral therapies used in this trial have no known serious adverse events and are consistently more efficacious than control conditions in treatment-seeking participants. The effect sizes of the behavioral therapies in this trial are in the

moderate range. Furthermore, any interim analysis and decision to stop the trial would likely be based on underpowered data and susceptible to error.

Oversight and Monitoring

Scientific advisory committee

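### The planned check cannot tell missing-at-random from missing-not-at-random data, and no stated analysis tests how far the urine-screen abstinence result depends on that difference

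*Combined protocol and SAP*

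**What the plan says.** All references are to the combined protocol and SAP.

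- **Analysis of non-adherence and missing data.** The team starts with description: "We will first describe the extent and patterns of missingness within each variable". It will then "check for associations between missing and observed data to determine the mechanism of missingness", listing missing completely at random (MCAR), at random (MAR) and not at random (MNAR) as candidates. Multiple imputation follows: "Appropriate imputation techniques will be chosen for the type of missing data and the statistical tools employed". The one sensitivity analysis is: "For sensitivity analysis, we will conduct analyses with and without multiple imputations".
- **To assess effectiveness.** The model is a mixed-effects model with intervention indicators, "time of the assessment (baseline, 13-, 26-, and 49-weeks), and intervention indicators-by-time interaction terms". The estimation method is not named.
- **Definition of effectiveness measures.** Primary outcome 3 is "reduction in methamphetamine use at 13-, 26- and 49-weeks measured by UDS (point abstinence"), together with self-reported abstinence. Screens are taken "in urine twice a week throughout the intervention period and at Week 49".
- **Randomization and Interventions.** Four consecutive negative screens in weeks 11 and 12 define a responder. "Others are considered non-responsive". This rule assigns second-stage treatment. It does not say how a missing screen counts in the outcome.
- **Sample size determination.** The plan allows 20% attrition, which it calls conservative, and anticipates 80% to 90% substance use as a base rate.

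**The concern.** MAR and MNAR differ in whether missingness still depends on the unseen value once the observed data are taken into account. No check on observed data can settle that. A reader told that the mechanism has been determined would be given an assurance the data cannot supply. If the type of missing data in the imputation sentence means its mechanism, the choice of imputation method would rest on that same check.

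The with/without comparison does not fill the gap. Standard multiple imputation and a likelihood-based mixed model on available data both assume MAR, so their agreement says little about MNAR.

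This bears on a primary outcome. If participants who are using give fewer screens, and do so more in one arm, the frontline comparison is biased, and no stated analysis would reveal by how much. Such a pattern is plausible in a trial of people who use methamphetamine, but the documents do not establish it.

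**Working it through.** The plan gives no figure for this point. Its 20% attrition input fits its power statement: 100 × (1 − 0.20) = 80 per group gives 79.4% power for a fall in use from 80% to 60% and 89.3% for 90% to 70% (pooled normal approximation, two-sided 5%).

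**Step 1: can the check identify the mechanism?** Suppose one arm has 20% of screens missing and 25% abstinence among those observed (assumed).
- Missing screens like observed ones: abstinence is 25%.
- Missing screens with twice the odds of being positive: abstinence among the missing is 0.25/(0.25 + 2 × 0.75) = 14.3%, so overall 0.8 × 25% + 0.2 × 14.3% = 22.9%.
- All missing screens positive: 0.8 × 25% = 20%.

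The observed data are identical in all three cases, so they cannot choose between them.

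**Step 2: how large could the bias be?** Assumptions: 300 per arm (600 split equally), no true difference, about 20% missing overall, analysis of observed screens, and more missing in the low-intensity arm. Let a be true abstinence, m the proportion missing, and OR the odds of a positive screen, missing versus observed. Observed abstinence p solves

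(1 − m)p + m·p/(p + OR(1 − p)) = a;

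if all missing screens are positive, p = a/(1 − m).

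Cells show bias (high minus low intensity, percentage points) and the rejection rate of a two-sided 5% two-proportion z test.

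| Missing, high vs low | Missing screens | 80% use | 90% use |
|---|---|---|---|
| 20% vs 20% | any common OR | 0; 5.0% | 0; 5.0% |
| 18% vs 22% | OR = 2 | −0.4; 5.1% | −0.2; 5.1% |
| 15% vs 25% | OR = 2 | 21.41 − 22.45 = −1.04; 5.9% | 10.76 − 11.33 = −0.57; 5.5% |
| 10% vs 30% | OR = 2 | 20.92 − 23.00 = −2.08; 8.6% | 10.50 − 11.64 = −1.14; 7.0% |
| 15% vs 25% | all positive | 23.53 − 26.67 = −3.14; 12.5% | −1.57; 8.2% |
| 10% vs 30% | all positive | −6.35; 35.8% | −3.17; 18.4% |

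Swapping the arms reverses the sign. The 80% to 90% is a planning base rate, not a follow-up rate. At an assumed 50% use, OR = 2 gives −1.72 (15% vs 25%) and −3.44 (10% vs 30%), with rejection rates of 6.6% and 11.6%. If all missing screens were positive, 15% vs 25% would give 50/0.85 − 50/0.75 = 58.82 − 66.67 = −7.84.

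**Step 3: would the with/without comparison show it?** Impute by arm from one earlier, fully observed screen with the same marginal rate and an assumed correlation of 0.5 to 0.7 with the outcome. For the 15% vs 25% and 10% vs 30% splits at 80% to 90% use, about 46% to 73% of the bias remains. For example, −1.04 becomes −0.76 at correlation 0.5 and −0.51 at 0.7. With OR = 2, the comparison moves by 0.15 to 1.1 points while 0.3 to 1.5 points stay hidden. If all missing screens are positive, it moves by 0.5 to 3.3 points while 0.7 to 4.5 stay hidden. It may hint at a problem but cannot measure what is left.

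**Step 4: is missing-as-positive a cure?** It estimates abstinence as (1 − m)p. In the OR = 2 cases at 80% use:
- 15% vs 25%: 0.85 × 21.41 − 0.75 × 22.45 = 18.20 − 16.84 = +1.4 points, against −1.0 from observed screens.
- 10% vs 30%: 0.90 × 20.92 − 0.70 × 23.00 = 18.83 − 16.10 = +2.7, against −2.1.

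At 50% use it gives +4.0 and +7.9, against −1.7 and −3.4. The true difference is zero throughout, so here the rule reverses the sign and enlarges the bias.

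**The case against.** **The plan recognises MNAR.** It lists it as a possibility and leaves the technique open, citing sources not available here. This stands: a reader might infer that the plan excludes MNAR methods, and the text does not support that. What can be said is that none is stated, so none is pre-specified. That both planned analyses assume MAR is likewise an inference about standard methods.

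**The plan already reaches differential missingness.** A reader might infer that missingness will not be examined by arm and time. That is not supported either. Arm and time are observed data, so the planned look at patterns and associations can include them. An explicit table of missing screens by arm and assessment is a matter of presentation.

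**The large figures depend on chosen inputs.** This stands. The documents give no gap in missingness between arms, the direction is assumed, and actual attrition may fall below 20%. With twice-weekly screens in the imputation model, more bias could be removed: at an assumed effective correlation of 0.85, about a quarter remains. That help is weaker at week 49, or when earlier screens are missing too.

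**Other data exist.** Self-reported abstinence is also part of primary outcome 3 and could serve as auxiliary information. It does not replace an MNAR analysis of the screens.

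**Conclusion.** Two points hold on the text. The plan claims to determine a mechanism that observed associations cannot determine, and it states no MNAR analysis for UDS abstinence. The responder rule, the mixed model, the intention-to-treat statement and the COVID-19 response text do not supply one.

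The size of any resulting bias is unknown. With no true difference it is zero when missingness and its relation to use are equal across arms. It is about 0.2 to 0.4 points, with type I error near 5.1%, for 18% versus 22% missing with doubled odds at the planning rates. At those rates it reaches several points only under large assumed arm differences, mainly when all missing screens are also positive. It could be larger if use at follow-up is well below 80%.

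A reader might infer that the frontline comparison will be materially biased, or biased against high intensity. The documents do not support that: they establish neither unequal missingness nor its direction. The case for changing the plan is that the present sensitivity analysis cannot answer the question and a suitable one is cheap. It should be made before outcome data are examined by arm.

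**What to change.** 1. Reword the check: it describes missingness, including UDS by arm and assessment time, and guides the choice of predictors for a MAR imputation model. Drop the claim to determine the mechanism.
2. Keep multiple imputation as the main analysis and name the earlier twice-weekly screens as predictors.
3. Instead of relying on the with/without comparison, pre-specify a delta-adjusted (tipping-point) analysis of UDS abstinence. Shift the odds of a positive screen among the missing separately in each arm, over a grid fixed in advance that starts at no shift (MAR). Report the shift at which the conclusion changes.
4. Missing-as-positive may be added only as a labelled extreme scenario, not as a better estimate. Step 4 of the working shows why. In addition, the COVID-19 section describes clinic closures, which can cause screens to be missed for reasons unrelated to use.

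The cost is a few sentences in the analysis plan and modest programming on data already being collected, with no effect on conduct. The downside is that the conclusion may read as less firm if a small shift overturns it.

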The study scientific advisory committee members include researchers, policy makers and activists working in HIV and addiction medicine fields in the U.S. and Vietnam. The scientific advisory committee meets once a year to review research progress and key findings, as well as discuss challenges to study implementation and plans to solve these challenges.

Data monitoring committee

Our data monitoring committee is composed of members of the Data and Safety Monitoring Board for Addiction Medicine (DSMBAM) of the University of California – Los Angeles. These members are not connected to the study in any way. The DSMBAM is independent from the National Institute on Drug Abuse (NIDA) – the sponsor of this study. The DSMBAM meets quarterly to monitor subjects' progress in the trial and considers whether adverse social harms (e.g., police detention, hospitalization due to overdose) differentially accrue by condition. Although there are no prospective stopping rules for this trial, the DSMBAM is within its charge to review aggregate data, request statistical tests of differences in social or other harms, and then advise changes in intervention type or intensity if statistically significant differences emerge in adverse events by condition. Prior to each meeting, the study team will submit a performance report including all reports of SAEs for DSMBAM's consideration. After each meeting, recommendations will be made in writing to the principal investigators.

Auditing trial conduct

Hanoi Medical University and the staff in the STAR-OM study provide oversight of financial management. The Vietnam teams and U.S. teams maintain frequent communication via emails and bi-weekly online meetings to report updates on the study progress, discuss scientific aspects of the study, and troubleshoot issues when they arise. The teams in Hanoi and HCMC meet online once weekly and in-person quarterly during monitoring visits to discuss the study conduct. We submit annual research progress reports to the Ethics Committee of Hanoi Medical University. Any protocol amendments need to get ethical approval before implementation. The UCLA Addiction Medicine Data Safety Monitoring Board independently review our data and data management twice a year.

Adverse event reporting and harms

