Adverse events in this trial are defined as medical issues that do not require hospitalization. Serious adverse events are defined as life-threatening events such (e.g. suicide, opioid overdose) or other events that have a negative impact on participants' life such as incarceration or compulsory drug rehabilitation. The clinic staff will communicate information about adverse events and serious adverse events to the study team right after they are informed by participants or participant families. The study coordinators in Hanoi and HCMC are responsible to report adverse events within 7 days and serious adverse events within 24 hours on REDCap with the time of onset, seriousness, duration, and outcomes. The principal investigator will decide what serious adverse events need to be reported to the Ethics Committee.

Plan for communicating important protocol amendment to relevant parties

We will first seek advice of our scientific advisory committee for all protocol amendments. Protocol amendments will undergo the review of Ethics Committee. If they are approved, we will notify the trial funder about these amendments. No protocol modifications will be implemented without ethical approval. Notification of the approved modifications will be forwarded to all study team members.

Dissemination plans

Results of this study will be published in peer-reviewed scientific articles and presented at international and regional conferences. We will organize dissemination workshops to communicate the study results to policy makers and healthcare professionals at the end of the trial. The de-identified datasets, statistical code, and full protocol are available from the first author upon reasonable request.

Ethics and Confidentiality

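### Medical admissions that are not life-threatening are excluded from adverse events and not named as serious, so whether they are reported depends on interpretation

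*Combined protocol and SAP*

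**What the plan says.** The section on adverse event reporting and harms sets two categories.

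- **Adverse events:** "Adverse events in this trial are defined as medical issues that do not require hospitalization".
- **Serious adverse events, first limb:** "Serious adverse events are defined as life-threatening events such (e.g. suicide, opioid overdose").
- **Serious adverse events, second limb:** "other events that have a negative impact on participants' life such as incarceration or compulsory drug rehabilitation".

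Clinic staff pass what they learn to the study team. The coordinators in the two cities must then "report adverse events within 7 days and serious adverse events within 24 hours on REDCap". The principal investigator decides which serious events go to the Ethics Committee.

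The section on the data monitoring committee describes what the board does and receives. It "considers whether adverse social harms (e.g., police detention, hospitalization due to overdose) differentially accrue by condition". Before each meeting "the study team will submit a performance report including all reports of SAEs for DSMBAM's consideration". The same section says there are no prospective stopping rules.

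**The concern.** Hospitalisation sets the upper limit of the adverse event category, but it is not used to open the serious category. A participant admitted with a condition that does not threaten life is outside the first definition by its own terms. That participant enters the second only if someone judges that the admission harmed the participant's life in the sense meant, and the two examples given for that limb are legal or social.

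This reverses the usual order of certainty. A minor complaint treated without admission has a definite category and a 7-day clock. A more severe event, an admission, has neither for certain.

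What is at stake is the comparison of harms by condition. No interim analysis is planned and there are no stopping rules, so the board is the main safeguard. The section on randomization and interventions says that counselors, research assistants and data managers know the allocation. A discretionary classification could therefore be applied differently by arm, without anyone intending it.

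**Working it through.** No arithmetic applies. The point depends on definitions and reporting routes, and the plan gives no figure to reproduce. The check takes each kind of event through the two definitions and then to the board.

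| Event | Adverse event? | Serious adverse event? | Clock | Named route to the board |
|---|---|---|---|---|
| Medical issue, no admission, not life-threatening | Yes | Not normally | 7 days | Not named |
| Life-threatening event, including opioid overdose | Not relevant | Yes, first limb | 24 hours | Yes, serious event report |
| Incarceration or compulsory rehabilitation | Not relevant | Yes, second limb by example | 24 hours | Yes, serious event report |
| Medical admission, not life-threatening | No, expressly excluded | Only if read into the second limb | 24 hours if so read, otherwise none | Only if so read |

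Only the last row is unsettled. Three further steps test whether something else in the document settles it.

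1. **Another classification rule.** Hospitalisation is mentioned in two places in the safety text: the adverse event definition, and the board's list of social harms, where it is limited to admission for overdose. Neither says how other admissions are classified.
2. **The board's wider powers.** The data monitoring committee section adds that "the DSMBAM is within its charge to review aggregate data, request statistical tests of differences in social or other harms". This lets the board look beyond serious event reports, but only at events that someone recorded.
3. **Other data sources.** The assessment schedule collects cost data, including other healthcare costs, and these may pick up some admissions. Nothing in the plan sends them to safety review.

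Such admissions are foreseeable. The plan is to enrol 600 participants, 200 of them HIV-positive, and to follow them to Week 49. The clinic physician's duties include referral to HIV and psychiatric services, and the section on COVID-19 modifications records confirmed cases among clinic patients. No admission rate is given, so no expected count can be derived.

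**The case against.** The case against has four parts.

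- **The second limb is open.** Its two events are introduced as examples, and an admission can reasonably be called an event with a negative impact on a participant's life. This stands. A reader might infer that, taken literally, the definitions give staff no category and no clock for an admission, so that every such admission is missed. The text does not support that: leaving an admission out requires a narrowing inference from the examples.
- **The structure suggests the intent.** Using hospitalisation as the ceiling for adverse events implies that admitted cases were meant to be serious. This is plausible, but the intent is not written down, and the phrase that would carry it has no threshold.
- **The board's remit is narrower than it may look.** A reader might infer that the board is charged with comparing all hospitalisation by condition and would see only life-threatening admissions. The remit names only admission for overdose, as an example, and opioid overdose is already an example of a serious event. That inference falls away.
- **The route is broader than serious event reports.** The pre-meeting report includes those reports and is not limited to them. The section on auditing trial conduct adds a twice-yearly independent review of data and data management. Formal entry in REDCap is made by coordinators in two cities, not by 20 clinics separately. All of this stands and limits the scope for inconsistency. It does not help with an event that clinic staff did not recognise as reportable and so did not pass on.

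The plan also says the behavioural therapies have no known serious adverse events. That bears on how many differences to expect between arms, not on whether the categories are complete.

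**Conclusion.** The point holds as an ambiguity in safety capture. Medical events requiring admission are expressly removed from one category and not named in the other. Admissions that are not life-threatening may therefore be classified inconsistently or left unrecorded, and unrecorded events cannot reach the board.

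The size is unknown. The events at risk are the non-life-threatening medical admissions among 600 participants up to Week 49, excluding opioid overdose. Of these, only the ones that staff do not read into the second limb would be lost. The documents give no figure for either quantity. They do not show that any event has been or would certainly be lost, nor that a loss would differ by arm. No effectiveness outcome or sample-size figure depends on this point.

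The conclusion assumes that no separate reporting manual or REDCap form, outside the documents reviewed, already lists hospitalisation as a seriousness criterion. If one does, the protocol needs only to be brought into line with it. The change is worth making because the wording is easily corrected and the board's comparison of harms depends on complete recording.

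**What to change.** In the section on adverse event reporting and harms, make the two reporting categories exhaustive:

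- State that any medical event requiring hospitalisation is a serious adverse event on the existing 24-hour pathway, alongside the events already listed.
- State that all other medical issues that are not serious remain adverse events on the 7-day pathway.

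In the section on the data monitoring committee, align the list of harms the board reviews with these categories, so that admissions for any medical cause are visible by condition.

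The cost is a short amendment with ethics review, a changed label on the REDCap form, a brief notice to clinic staff and coordinators, and slightly more serious event reports. The change concerns reporting only and alters no treatment or clinical rule.
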